5.1. Primary Efficacy Endpoint

The primary endpoint of this study is the percentage of patients achieving complete corneal healing of PED or corneal ulcer at Week 8, defined as no corneal fluorescein staining in the area of the PED or corneal ulcer as assessed by an independent central reading centre.

5.2. Key Secondary Efficacy Endpoint

The key secondary endpoint of this study is the percentage of patients achieving complete corneal healing of PED or corneal ulcer at Week 8, defined as no corneal fluorescein staining in the area of the PED or corneal ulcer and no persistent staining outside of corneal lesion elsewhere in the cornea (i.e. not changing in shape and/or location at different timepoints) as assessed by an independent central reading centre.

5.3. Secondary Efficacy Endpoints

- Percentage of patients who achieve a 5-, 10-, and 15-letter mean improvement in BCDVA by the ETDRS chart at Week 8 compared to baseline (in all patients and in patients with a central location of the PED or corneal ulcer, respectively).
- Percentage of patients achieving complete corneal healing of PED or corneal ulcer at Week 8, defined as no corneal fluorescein staining in the area of the PED or corneal ulcer as assessed by the investigator.
- Time to complete corneal healing of PED or corneal ulcer defined as no corneal fluorescein staining in the area of the PED or corneal ulcer as assessed by an independent central reading.
- Time to complete corneal healing of PED or corneal ulcer defined as no corneal fluorescein staining in the area of the PED or corneal ulcer as assessed by the investigator.
- Percentage of patients having deterioration of the disease at Week 8 (defined as increase in lesion size ≥ 1 mm compared to baseline as assessed by the investigator, or mean decrease in BCDVA by > 5 letters compared to baseline, or progression in lesion depth to corneal melting or perforation, or onset of infection).
- Mean change in BCDVA from baseline to Week 8 in all patients and in patients with a central location of the PED or corneal ulcer, respectively.
- Percentage of patients with improvement in corneal sensitivity from baseline as measured by Cochet-Bonnet aesthesiometer at Week 8.

5.4. Other Efficacy Endpoints

- Percentage of patients achieving complete corneal healing of PED or corneal ulcer at Week 8, defined as the greatest diameter of corneal fluorescein staining in the area of the PED or corneal ulcer < 0.5 mm as assessed by central reading.
- Percentage of patients achieving complete corneal healing of PED or corneal ulcer at Week 8, defined as the greatest diameter of corneal fluorescein staining in the area of the PED or corneal ulcer < 0.5 mm as assessed by the investigator.

This document is confidential.

Filing requirements: TMF

- Percentage of patients achieving complete corneal clearing at Week 8, defined as a score of 0
 using the Oxford scale.
- Time to at least 50% corneal healing (defined as a ≥ 50% reduction in the greatest diameter of the lesion) as determined by central reading.
- Time to at least 50% corneal healing (defined as a ≥ 50% reduction in the greatest diameter of the lesion) as determined by the investigator.
- Time to onset of healing (defined as a > 20% reduction in the greatest diameter of the lesion) as determined by central reading.
- Time to onset of healing (defined as a > 20% reduction in the greatest diameter of the lesion) as determined by the investigator.

5.5. Other Exploratory Endpoints

- Change from baseline in QoL evaluated using the NEI VFQ-25.
- Change from baseline in the overall NRS score for ocular symptoms and tolerability.

5.6. Pharmacokinetic Analyses

For the first 24 patients, the C_{max} , C_{max} ss, T_{max} , T_{max} , AUC_{0-4} (Day 1), AUC_{τ} (Day 7) and AUC_{0-t} PK parameters will be assessed according to the following sampling schedule :

- On Day 1 and Day 7: predose, 10, 20 and 40 minutes and 1, 2, and 4 hours and 8 hours, if applicable, after the 1st daily administration (last sampling before next dose);
- On Day 1 and Day 7: at 20 minutes and 4 hours after the 2nd daily administration
- On Day 28 and Day 56: at 4 hours postdose and before the next REC 0/0559 administration

For all patients, Ctrough:

• On Day 28 and Day 56: at 4 hours postdose and before the next REC 0/0559 administration

5.7. Safety Analyses

Safety assessments will be conducted for all patients from the Screening Visit (upon the signature of the ICF) to the end of the study.

Safety assessments include physical examination, ophthalmological examination, vital signs, 12-lead ECG, laboratory safety tests, and AE recording (including serious AEs [SAEs] and adverse events of special interest [AESI] as described in the protocol, Section 12).

6. Analysis Sets

6.1. Enrolled Population

The enrolled population will include all individuals who signed the informed consent form (ICF), including screen failures and patients randomised but not treated. Unless specified otherwise, this set will be used for all patient listings and the summary table of patient disposition.

6.2. Safety Population (SAF)

The safety population will include all randomised patients who receive at least 1 dose of study drug. The treatment group assignment in this population will be defined by the treatment actually received. This population will be used for the analysis of safety.

6.3. Modified Intent-to-Treat Population (mITT)

The modified intent-to-treat population will include all patients who are randomised and receive at least 1 drop of study drug, irrespective of any deviation from the protocol or premature discontinuation. The treatment group assignment will be designated according to initial randomisation. The mITT population will serve as the basis for the analysis of efficacy.

6.4. Per Protocol (PP) Population

The per-protocol population will include all patients in the mITT population for whom no major protocol violations/deviations occurred. Patients will be analyzed according to randomised treatment.

Criteria for exclusion from the PP population will be determined at the blinded data review meeting (BDRM) shortly before the database lock at the end of the study. All protocol deviations (PDs) will be tracked during the study and reviewed at the BDRM. The BDRM will be performed according to SOP 3911.

6.5. PK Population (PK)

For PK analysis all patients included in the mITT and having at least one plasma concentration of study drug measured will be included. Subjects with insufficient number of PK samples to derive PK parameters may still be used for listing and summary of PK concentrations.

6.6. Protocol Deviations

Major protocol deviations, as determined by a review of the data prior to DB lock, will result in the exclusion of a subject from the PP population. All deviations/scenarios that arise during the BDRM will be documented and reported in the protocol deviations log. The details of handling protocol deviations and non compliances (PDNC) are specified in the PDNC management plan of this study.

6.7. Sub-Populations

At the time of the BDRM sub-populations may be defined based on data availability and will be described in the Blind Data Review and Analysis Sets Report following the decisions of the BDRM before database lock.

7. Estimands

7.1. Estimands for the Primary Efficacy Endpoint

The primary efficacy endpoint is the evaluation of the percentage of patients achieving complete corneal healing of PED or corneal ulcer at Week 8, defined as no corneal fluorescein staining in the area of the PED or corneal ulcer as assessed by an independent central reading centre, and the population level summary will be the difference in treatment proportions (common risk difference) at Week 8. The primary estimand for the primary efficacy endpoint will be evaluated in the mITT population, which is patients with stage 2 or stage 3 NK as defined by the inclusion/exclusion criteria who received at least one dose of study drug.

Intercurrent events are events occuring after treatment initiation that affect the interpretation of or the existence of the measurements associated with the clinical question of interest. As more than one intercurrent event is possible, Table 3 lists all potential intercurrent events and the strategy to deal with them.

Table 3: Potential intercurrent events for the primary estimand

Intercurrent Event	Primary estimand: Strategy to Deal With Intercurrent Event Within Analysis	Primary estimand: Assessment of Patient
ICE1: Treatment discontinuation due to treatment-related AE	Composite	Available data observed on or after the occurrence of the ICE will be set to missing and imputed as failure.
ICE2: Treatment discontinuation due to any other reason than treatment-related AE or death	Treatment policy strategy	Available data occurring on or after the ICE will be used for the analysis as observed. Monotone missing data will be imputed using LOCF
ICE3: Prohibited rescue treatments or rescue procedures initiation during the 8 week study treatment administration period	Composite	Available data observed on or after the occurrence of the ICE will be set to missing and imputed as failure.
ICE4: Death	Composite	All monotone missing data will be imputed as failure.

For patients who discontinue treatment due to a treatment-related AE (ICE1), due to strat of prohibited rescue treatments or rescue procedures during the 8 week study treatment administration period or due to death (ICE4) a composite strategy will be applied. All observed data occurring on or after ICE1 and ICE3 will be set to missing and imputed as failure. Prohibited rescue treatment or rescue procedures starting at

or after the visit evaluation will not be considered as ICE for the analysis (Table 3). In case of treatment discontinuation due to death (ICE4) the subsequently missing efficacy assessment will be imputed as failure.

7.1.1. Supplementary Estimands of the Primary Efficacy Endpoint

The primary efficacy endpoint is the evaluation of the percentage of patients achieving complete corneal healing of PED or corneal ulcer at Week 8, defined as no corneal fluorescein staining in the area of the PED or corneal ulcer as assessed by an independent central reading centre, and the population level summary will be the difference in treatment proportions (common risk difference) at Week 8. The supplementary estimand for the primary efficacy endpoint will be evaluated in the mITT population, which is patients with stage 2 or stage 3 NK as defined by the inclusion/exclusion criteria who received at least one dose of study drug.

Table 4 lists all potential intercurrent events and the strategy to deal with them.

Table 4: Potential intercurrent events for the supplementary estimand

Intercurrent Event	Supplementary estimand: Strategy to Deal With Intercurrent Event Within Analysis	Supplementary estimand: Assessment of Patient
ICE1: Treatment discontinuation due to treatment-related AE	Treatment policy strategy	Available data occurring on or after the ICE will be used for the analysis as observed. Any monotone missing data will be imputed under MAR assumption.
ICE2: Treatment discontinuation due to any other reason than treatment-related AE or death	Treatment policy strategy	Available data occurring on or after the ICE will be used for the analysis as observed. Any monotone missing data will be imputed under MAR assumption.
ICE3: Prohibited rescue treatments or rescue procedures initiation during the 8 week study treatment administration period	Treatment policy strategy	Available data occurring after the ICE will be used for the analysis as observed. Any monotone missing data will be imputed under MAR assumption.
ICE4: Death	Composite strategy	All monotone missing data after the occurence of the ICE are imputed as failure.

This document is confidential.

Controlled Document ID: **3903A.02**, Effective Date 31-Aug-2020 Filing requirements: TMF

The approach for the supplementary estimand assumes that for patients discontinuing study treatment because of treatment-related AEs (ICE1), any reason other than treatment-related AEs and death (ICE2) and prohibited rescue treatments or rescue procedures during the planned 8 week study treatment administration period (ICE3) a non-confounded estimate of the treatment effect is provided. Therefore the treatment policy strategy will be applied and any missing assessment of complete corneal fluorescein staining will be imputed by MI assuming missing at random (MAR). Patients will be imputed based on their treatment group and randomization strata (NK stage and region).

In case of treatment discontinuation due to death (ICE4) a composite strategy will be applied where the subsequently missing efficacy assessment will be imputed as failure, regardless of treatment group or randomisation strata.

More details on the multiple imputation approaches are provided in Section 8.3.

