4.3. Determination of Sample Size

A total of 108 patients will be randomly assigned to 1 of the 3 active treatment arms or the vehicle treatment arm (27 patients per arm). Randomisation will be stratified by disease stage (Stage 2, Stage 3) and region (Europe, North America).

Considering an estimated response rate of 27% for the vehicle treatment arm based on studies conducted in a similar patient population with cenegermin (Oxervate) and with approximately 80% of power and a 2-sided alpha of 0.05, the sample size of 27 patients per group (including a 15% estimate of dropout rate) should allow analysis to show a difference of at least 45% between the active treatment arms and the vehicle treatment arm.

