7.2. Estimands for the Secondary, Other and Exploratory Efficacy Endpoints

The estimands framework for the primary efficacy endpoint will apply for the secondary, other and exploratory efficacy endpoints related to the secondary efficacy objective, other efficacy objectives and other exploratory efficacy objectives, for all visits up to and including Week 8. This includes the definitions of the intercurrent events (Table 3) as well as their imputation methods for all binary endpoints.

For all continuous efficacy endpoints the definitions of the intercurrent events, strategies to handle the intercurrent events and imputation methods are detailed in Table 5.

Table 5: Potential intercurrent events for continuous endpoints

Intercurrent Event	Estimand: Strategy to Deal With Intercurrent Event Within Analysis	Estimand: Assessment of Patient
ICE1: Treatment discontinuation due to treatment-related AE	Hypothetical	Available data occurring on or after the ICE will be not be used for the analysis and set to

		missing. Monotone missing data will be imputed assuming MNAR.
ICE2: Treatment discontinuation due to any other reason than treatment-related AE or death	Treatment policy strategy	Available data occurring on or after the ICE will be used for the analysis as observed. Monotone missing data will be imputed assuming MAR
ICE3: Prohibited rescue treatments or rescue procedures initiation during the 8 week study treatment administration period	Hypothetical	Available data occurring on or after the ICE will be not be used for the analysis and set to missing. Monotone missing data will be imputed assuming MNAR.
ICE4: Death	Composite	Worst-case data imputation, i.e., BCDVA worst value in surviving patients

Patients who discontinue due to treatment-related AEs (ICE1) will be assumed to confound the estimate of the treatment effect and therefore is assumed have a similar outcome over time as the vehicle group under a hypothetical setting. Therefore assessments after treatment discontinuation due to treatment-related AEs will be set to missing (if not already missing) and will be imputed under the MNAR assumption using a control-based pattern approach with vehicle group as reference and randomisation strata (NK stage and region) included.

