For patients discontinuing study treatment because of any reason other than treatment-related AEs and death (ICE2), a non-confounded estimate of the treatment effect is provided. Therefore the treatment policy strategy will be applied and any missing assessment will be imputed by MI assuming MAR. Patients will be imputed based on their treatment group and randomization strata (NK stage and region).

For patients who start rescue treatments or rescue procedures during the planned 8 week study treatment administration period used for treatment of NK (ICE3), a confounded estimate of the treatment effect is assumed. Therefore the estimand allows for the assessment of the treatment effect in a hypothetical setting, assuming a similar outcome over time, as expected under vehicle administration. Assessments after the start of the rescue treatments or rescue procedures will be set to missing (if not already missing) and will be imputed under the assumption of MNAR using a control-based pattern approach with the vehicle group as reference and randomisation strata (NK stage and region) included.

In case of treatment discontinuation due to death (ICE4) a composite strategy will be applied where the subsequently missing efficacy assessment will be imputed with the worst value single imputation approach, regardless of treatment group or randomisation strata (NK stage and region).

All time to event efficacy endpoints, definitions of the intercurrent events, strategies to handle the intercurrent events and imputation methods are detailed in Table 6.

Table 6: Potential intercurrent events for time to event endpoints

Intercurrent Event	Estimand: Strategy to Deal With Intercurrent Event Within Analysis	Estimand: Assessment of Patient
ICE1: Treatment discontinuation due to treatment-related AE	Composite	Available data observed on or after the occurrence of the ICE and up to week 8 (day 56) will be set to missing and imputed as failure. The patient will be censored at the end of week 8 (day 56) of the study treatment administration period.
ICE2: Treatment discontinuation due to any other reason than treatment-related AE or death	Treatment policy strategy	Available data occurring on or after the ICE will be used for the analysis as observed. Monotone missing data will be imputed using LOCF up to week 8 (day 56).

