Missing efficacy assessment data due to intercurrent events will be handled according to the strategies as described in the estimand Section 7. All efficacy analyses using the primary estimand framework for definitions of ICEs and the strategies to deal with them, will be imputed via single value imputation, i.e. as failure/non-responder or LOCF.

For all parameters that need to be imputed using multiple imputation, ranges (minimum and maximum values) and decimal rounding will be specified as applicable. In total 20 imputed datasets will be created per parameter and visit (proc mi).

All intermittent missing efficacy assessment data will be multiple imputed under MAR assumption using a Markov Chain Monte Carlo (MCMC) approach for all endpoints where MI is required.

Once the monotone missing data pattern is obtained the remaining missing values (whether missing due to ICE or not) will be imputed. Missing efficacy assessment data that are missing without the definition of an ICE met, will be multiple imputed under MAR assumption with either a monotone linear regression for continuous parameters or monotone logistic regression for categorical parameters, as applicable. Treatment group and randomisation strata will be included.

For the supplementary estimand strategy and first sensitivity analysis of the primary endpoint as well as for the continuous secondary efficacy endpoints multiple imputation will be applied for missings due to intercurrent events as follows:

- MNAR: multiple imputation will be performed based on the assumption of MNAR with a controlbased pattern approach and vehicle as reference group. Randomisation strata will be included. Categorical parameters will be imputed using a monotone logistic regression and continuous parameters will be imputed with monotone linear regression, as applicable.
- MAR: multiple imputation will be used to impute continuous parameters with monotone linear regression and categorical parameters with monotone logistic regression, as applicable. Treatment group and randomisation strata are included.
- Composite strategy: efficacy assessments that are not performed because of treatment discontinuation due to death will be imputed with worst value or failure/non-responder single imputation approach.

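### The supplementary treatment-policy estimand fills readings missing after a drug-related stop or a rescue from mainly on-drug patients, which can overstate the active effect and is not tested

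*SAP*

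**What the plan says.** SAP 7.1.1 and Table 4 define the supplementary estimand on the mITT population, summarised by the common risk difference at Week 8. ICE1, ICE2 (stopping for other reasons) and ICE3 all get a treatment-policy strategy. Readings collected after the event count as observed. For the rest, "any missing assessment of complete corneal fluorescein staining will be imputed by MI assuming missing at random (MAR"), using assigned treatment and the two randomisation strata. The stated ground is the assumption that for these patients "a non-confounded estimate of the treatment effect is provided".

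SAP 8.3.2 gives the matching general rule: MAR imputation handles "categorical parameters with monotone logistic regression, as applicable. Treatment group and randomisation strata are included". The footnote to shell Table 14.2.1.2 repeats MAR for ICE1 to ICE3.

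For continuous endpoints, SAP 7.2 starts from the other side. On ICE1: "Patients who discontinue due to treatment-related AEs (ICE1) will be assumed to confound the estimate of the treatment effect". On ICE3: "a confounded estimate of the treatment effect is assumed". Both are then imputed with vehicle as the reference group, under a strategy that Table 5 labels hypothetical.

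The primary estimand (SAP 7.1, Table 3) scores ICE1 and ICE3 as failures, and SAP 10.1.1 bases confirmatory inference on it alone.

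**The concern.** A treatment-policy estimand asks what happens to patients whether or not they stay on drug. If a patient stops for a related adverse event and is not seen at Week 8, the missing value is an off-drug outcome. A model with only assigned arm and strata predicts it from everyone observed in that arm, most of whom would still be taking the drops. For the missing readings, the label says treatment policy while the model comes close to asking what would have happened had the patient continued.

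No planned analysis probes this for ICE1 or ICE3. The first sensitivity analysis (SAP 7.1.2) uses a control-based model for ICE2 only. The second (7.1.3) uses observed cases and so drops these patients when Week 8 is missing. The per-protocol analysis (7.1.4) reuses the primary rules. The reader therefore sees two treatments of these missing readings, failure or own-arm MAR, with nothing in between. If the supplementary estimate is read as reassurance about the failure rule, part of that reassurance may come from the imputation model.

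**Working it through.** **Inputs from SAP 4.3.** "Considering an estimated response rate of 27% for the vehicle treatment arm"; "a difference of at least 45% between the active treatment arms and the vehicle treatment arm", so 72% on active; "approximately 80% of power and a 2-sided alpha of 0.05"; 27 per arm including 15% dropout.

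**The plan's own figure.** The two-proportion formula with continuity correction for 27% against 72% gives 23 evaluable per arm. Then 23 / 0.85 = 27.06, which is 27 by rounding (28 if rounded up). Exact Fisher power at 23 per arm is 82.8%. The sample size reproduces and is not at issue. The 27% and 72% serve below as planning values only.

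**Per patient, last seen unhealed.** Assume constant healing rates. The chance of healing by Day 56, given unhealed on Day d, is 1 − 0.28^((56−d)/56) at the active rate and 1 − 0.73^((56−d)/56) at the vehicle rate. The shift in an arm of 27 is the difference divided by 27.

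| Last seen unhealed | Own-arm MAR | Vehicle rate | Shift in arm of 27 |
|---|---|---|---|
| Day 7 | 67% | 24% | 1.6 points |
| Day 14 | 62% | 21% | 1.5 points |
| Day 21 | 55% | 18% | 1.4 points |
| Day 28 | 47% | 15% | 1.2 points |

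This requires earlier healing status to be in the model, which the SAP does not settle. If it is not, the draws are 72% and 27%, and the shift is 45 / 27 = 1.7 points per patient.

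**Per arm.** Let f be the share with ICE1 or ICE3, m the share of those missing at Week 8, p the on-drug rate and q the true rate after the event. Then

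bias = f·m·(r − q), with r = [(1−f)p + f(1−m)q] / (1 − f·m).

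The documents give no f, m or q, so all three are assumptions. With p = 72%, f = 15% (0.15 × 27, about 4 patients) and m = 1, r equals p:

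- q = 0: 0.15 × 72 = +10.8 points
- q = 27%: 0.15 × 45 = +6.75, about +6.8 points
- q = 50%: 0.15 × 22 = +3.3 points
- q = 72%: 0
- q = 90% (an effective rescue): 0.15 × (−18) = −2.7 points

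With half of these patients observed (m = 0.5), the range from q = 0 to q = 90% is +5.0 to −1.2 points. With f = 5% and m = 1 it is +3.6 to −0.9.

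**On the risk difference.**

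- Equal f = 15%, m = 1 and the same q in both arms: 0.15(72 − q) − 0.15(27 − q) = 0.15 × 45 = +6.75 points, whatever q is.
- Leavers on vehicle only, none healing: the vehicle rate is raised by 0.15 × 27 = 4.05, so the difference is understated by about 4.1 points.

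**The case against.** The best case for leaving the plan alone has four parts.

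First, only missing readings are imputed. Protocol 7.1 and 8.4.1 ask patients who stop drug or start rescue to attend all visits, and off-drug patients who do attend also inform the model. This stands and limits the size. It does not remove the problem, because the plan allows for 15% dropout and the protocol provides a shorter route, Early Termination and Follow-up, for those who cannot continue.

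Second, a treatment-policy outcome includes the effect of rescue, which may be topical, oral or surgical (Protocol 9.6.2) and may heal the eye. A reader might infer that active healing is overstated as a matter of fact. The documents do not support that: after rescue the sign is open, and rescue for worsening could be commoner on vehicle if the drug works. Four leavers in one active arm and none on vehicle would use up the whole 15% allowance in that arm, and Protocol 5.4 expects no specific safety concern with the drug.

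Third, a reader might infer that SAP 7.1.1 and 7.2 flatly contradict each other. They serve different estimands. Under a hypothetical strategy post-event data are discarded, and under treatment policy they are kept, so the premises may differ. What remains is narrower. For missing values, own-arm MAR amounts to assuming that an off-drug patient resembles an on-drug one, while 7.2 assumes the patient resembles vehicle. No reason is given for the difference.

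Fourth, a reader might conclude that Table 5's vehicle-reference model should simply replace MAR for both events. For a rescued patient, vehicle donors who are mostly unrescued are also a poor match, so that would exchange one counterfactual for another.

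**Conclusion.** The mismatch is real and confined to the supplementary estimand. Readings missing after ICE1 or ICE3 are modelled without regard to the event that defines them, and no sensitivity analysis covers the gap. The effect can be to overstate active healing and the risk difference. The argument is strongest for ICE1, where benefit may be lost on stopping and no rescue effect need be supposed.

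The illustrative sizes of 1.2 to 1.6 points per patient and about 6.8 points on the risk difference rest on the planning rates. The first also needs constant healing rates and a vehicle-like true outcome. The second also needs 15% of both arms affected, all missing, with equal later healing. Fewer events or better follow-up shrink both. For ICE3 the direction is uncertain, and if leavers are mainly on vehicle it can reverse. No confirmatory p-value depends on this analysis. The point is a worthwhile, cheap correction, not a threat to the trial's main conclusion.

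**What to change.** In SAP Table 4 and 8.3.2:

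1. Keep post-event readings as observed.
2. Impute readings missing after ICE1 with the control-based, vehicle-reference model.
3. For ICE3, keep MAR but add a control-based or tipping-point sensitivity analysis beside it, without making vehicle donors the rule.
4. State whether healing status at earlier visits enters the monotone logistic model, since that sets the size of any bias.
5. Reword the rationale in 7.1.1 so that it is consistent with 7.2, or explain why the assumption differs for this estimand.

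These changes should be made before unmasking. The control-based logistic model is already needed for the first sensitivity analysis, and its continuous counterpart for Table 5, so programming is small. The cost is SAP wording, one extra table, and a supplementary estimate that may be slightly less favourable to the drug.
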